Prophylactic Therapy: For patients randomized to emapalumab, prophylaxis for Herpes Zoster virus infection has to be in place from the day before initiation of emapalumab treatment until end of study Concomitant Therapy: Concomitant use of IL-6 inhibitors (e.g., tocilizumab), non-anakinra IL-1 inhibitors (e.g, canakinumab), TNF inhibitors and JAK inhibitors is not allowed. If any of these therapies are initiated at the discretion of the Investigator e.g., as rescue therapy due to worsening of the patient's condition, then the patient should be withdrawn from study. Hydroxychloroquine, chloroquine, glucocorticoid treatment, antimicrobial therapy and prophylaxis are not limited. Analgesic treatment, transfusion of blood products, electrolyte and glucose infusions, i.v. parenteral nutrition, positive inotropic support, antibiotics, antifungal and anti-viral treatments (e.g., remdesivir), ultrafiltration or hemodialysis, as well as general supportive care are permitted. The study will enroll a total of 54 patients, 18 per arm according to the 1:1:1 Determination of sample randomization. Patients will be stratified based on glucocorticoid treatment at size: randomization to ensure an equal distribution between treatment arms. The sample size has been estimated based on the following assumptions: An overall one-sided significance level for efficacy of 0.097 (9.7%) 1. and a power of 74% for each comparison under the assumption that the true success rates are 50% in the SoC group increasing to 80% in the emapalumab or anakinra groups. 2. The study will consist of two stages, with equal numbers of patients randomised into Stage 1 and into Stage 2 per treatment arm. 3. There is the potential to stop for futility of emapalumab or anakinra (or both) at the end of Stage 1. 4. The futility rule for stopping at the end of Stage 1 is binding.

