5.3.3 Withdrawal of patients from treatment or study

5.3.3.1 Withdrawal from treatment

A patient should be withdrawn from the study treatment if, in the opinion of the Investigator, it is medically necessary, or if it is the wish of the patient.

When a patient is withdrawn, the date of last IMP administration and the date and reason for treatment withdrawal should be clearly described in the relevant sections of the CRF. If a patient is removed from treatment because of an AE, the reason for treatment withdrawal should always be stated as 'adverse event' irrespective of whether this was the investigator's or the patient's decision.

The patient will continue to participate in the study without taking study treatment.

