5.3.3.2 Withdrawal from study

Whenever possible and irrespective of the reason for withdrawal, the patient should be examined as soon as possible. Relevant samples should be obtained and all relevant assessments should be completed, preferably according to the schedule for Visit 6 (Day 15). The CRF should be completed as far as possible. Date and reason for the study withdrawal should be clearly described in the CRF.

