5.4.7.2 Concomitant therapy

Concomitant use of IL-6 inhibitors (e.g., tocilizumab), non-anakinra IL-1 inhibitors (e.g, canakinumab), TNF inhibitors and JAK inhibitors is **not** allowed. If any of these therapies are initiated at the discretion of the Investigator e.g., as rescue therapy due to worsening of the patient's condition, then the patient should be withdrawn from study (see Section 5.3.3.2).

Hydroxychloroquine, chloroquine, glucocorticoid treatment, antimicrobial therapy and prophylaxis are not limited.

Analgesic treatment, transfusion of blood products, electrolyte and glucose infusions, i.v. parenteral nutrition, positive inotropic support, antibiotics, anti-fungal and anti-viral treatments (e.g, remdesivir), ultrafiltration or hemodialysis, as well as general supportive care are permitted.

Other therapy considered necessary for the patient's welfare may be given at the discretion of the Investigator.

For patients taking other treatments that are substrates for CYP450 with a narrow therapeutic index (e.g. warfarin and phenytoin), the treating physician should make appropriate treatment adjustments and monitor the patient as deemed necessary.

All relevant concomitant therapy, as defined by the Investigator, will be recorded in the CRF.

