5.5.3.8 Survival and hospital discharge

Data on survival and hospital discharge will be collected at Visits 7 (Day 28), Visit 8 and 9 (Weeks 6 and 10) and recorded in the CRF.

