5.5.4.3.2 Reporting of serious adverse events

All SAEs occurring after study drug initiation and up to the end of study visit (Visit 9, Week 10) must be reported on AE pages in the CRF and on an SAE form, regardless of the investigator-attributed causal relationship with study treatment.

Abnormal laboratory findings

Abnormal laboratory findings, if serious, must be reported on specific AE pages of the CRF.

Following laboratory variables are collected for the assessment of efficacy (see Section 6.5.3.2) at screening and during the treatment period, and are not required to be reported as SAEs as described above: WBC including differential counts, RBC, Hgb, platelet count, fibrinogen, complement C3/C4, PT-INR, and cardiac troponin; ALT, AST, total bilirubin, creatinine, ferritin, LDH, D-dimer, CRP, electrolytes (sodium, potassium, calcium), and glucose.

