5.5.4.3.3 Follow-up of serious adverse events

Serious adverse events still ongoing at the end of study visit (Visit 9, Week 10) must be followed up until resolution or stabilization, or until a definite event outcome is provided, e.g., resolved with sequelae or death.

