5.5.5 Exploratory assessments

5.5.5.1 Clinical Status

Data on clinical status based on a 7-point ordinal scale will be collected at Visits 1 to 9 and recorded in the CRF.

The scale consists of the following categories:

- 1. Death
- 2. Hospitalized, requiring invasive mechanical ventilation or extracorporeal membrane oxygenation (ECMO)
- 3. Hospitalized, requiring non-invasive ventilation or high flow oxygen devices
- 4. Hospitalized, requiring supplemental oxygen
- 5. Hospitalized, not requiring supplemental oxygen requiring ongoing medical care
- 6. Hospitalized, not requiring supplemental oxygen no longer requires ongoing medical care
- 7. Not hospitalized

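### Rescue with a prohibited cytokine or JAK inhibitor ends study participation, so survival and discharge are censored for worsening, and a patient who exits before ventilation is scored a primary success

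*Protocol*

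**What the plan says.** - **Rescue rule.** Protocol 5.4.7.2 bars IL-6, non-anakinra IL-1, TNF and JAK inhibitors. If the investigator starts one, "then the patient should be withdrawn from study (see Section 5.3.3.2" applies. The synopsis has the same instruction. Section 5.1 leaves investigators free to choose any rescue drug in any arm, and the trial is open-label (5.4.6).
- **What follows withdrawal.** Section 5.3.3.2 asks for a prompt examination at which "all relevant assessments should be completed, preferably according to the schedule for Visit 6 (Day 15" visit. It names no later contact. For a patient who only stops study drug, 5.3.3.1 says the opposite: "The patient will continue to participate in the study without taking study treatment".
- **Follow-up at stake.** Section 5.5.3.8: "Data on survival and hospital discharge will be collected at Visits 7 (Day 28), Visit 8 and 9 (Weeks 6 and 10"). Section 5.5.1.7 allows telephone contact at Weeks 6 and 10.
- **Other routes to the data.** Section 5.5.5.1: "Data on clinical status based on a 7-point ordinal scale will be collected at Visits 1 to 9". Section 5.5.4.3.2: "All SAEs occurring after study drug initiation and up to the end of study visit (Visit 9, Week 10) must be reported". Under 5.5.4.3.3, SAEs still ongoing at the Week 10 visit "must be followed up until resolution or stabilization, or until a definite event outcome is provided".
- **Censoring.** SAP 8.5.2 censors survival at the last date known alive. It censors discharge at the last date known hospitalized, with early discontinuation and death among its examples.
- **Primary scoring.** Protocol 7.3.8 and SAP 8.2.1 and 8.5.1 apply the early-discontinuation rule at treatment stop in the active arms and at study stop in standard of care (SoC). A patient who discontinues before Day 15 without ever starting IMV or ECMO is a success. Death by Day 15 is a failure.

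**The concern.** The trigger for leaving the study is typically clinical worsening, so the patients who lose follow-up are not a random subset. The planned Kaplan-Meier, log-rank and Cox analyses of survival and discharge assume censoring unrelated to prognosis. Because the trial is open-label, rescue may also differ by arm.

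The same exit affects the primary endpoint. A patient who worsens, is rescued and leaves before Day 15 without IMV or ECMO is scored a success. Later ventilation is not looked for, and only a death by Day 15 that becomes known reverses the score.

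In the emapalumab arm, new infections after a second immunosuppressant, mainly non-serious ones, may go unrecorded.

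**Working it through.** **1. Scheduled contacts lost (documents only).** Contacts fall on Days 28, 42 and 70. Exit before Day 28 loses 3 of 3, exit between Days 28 and 42 loses 2, and exit between Days 42 and 70 loses 1. Time to Day 70 without scheduled contact: exit on Day 5, (70-5)/70 = 93%; Day 10, (70-10)/70 = 86%; Day 28, (70-28)/70 = 60%.

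**2. Patients affected.** The documents give no rescue rate. Assuming 10% to 30%: 0.10 × 54 = 5.4 and 0.30 × 54 = 16.2, so about 5 to 16 patients.

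**3. Survival illustration (all inputs assumed).** Take an arm of 18 with 4 rescued on Day 5. Two of the rescued die (Days 12 and 22), as do 3 of the other 14 (Days 20, 25 and 30). True mortality is 5/18 = 27.8%. The Kaplan-Meier estimate depends on what is learned after exit:
- Nothing: 1 - 11/14 = 21.4%.
- Only the deaths, with the 2 rescued survivors censored on Day 5: 1 - 11/16 = 31.3%.
- Deaths, and rescued survivors known alive to Day 28: 1 - (14/18)(11/12) = 28.7%.

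In general, let r be the share rescued, m_r and m_o the mortality in rescued and other patients, and let all withdrawals precede all deaths. True mortality is r·m_r + (1-r)·m_o. The estimate is m_o with no capture, and true/(1 - r(1-m_r)) with deaths only. With m_r = 0.5 and m_o = 0.2:
- r = 0.1: true 23.0%; estimates 20.0% (-3.0 points) and 24.2% (+1.2).
- r = 0.3: true 29.0%; estimates 20.0% (-9.0) and 34.1% (+5.1).

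For scale, the exact 95% interval for 5/18 is 9.7% to 53.5%.

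**4. Discharge illustration (assumed, no deaths by Day 28).** Ten of 14 others and 1 of 4 rescued are discharged by Day 28. True 11/18 = 61.1%. With the 4 censored on Day 5, 10/14 = 71.4%, an error of +10.3 points.

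**5. Primary endpoint, current rule.** Exact enumeration of the two-stage design used 9 + 9 per arm, one-sided Fisher tests, efficacy at p < 0.025 then p < 0.159, and futility at p > 0.690. At 50% against 80% it gives 73.6% power, which reproduces the stated 74%. At 50% in both arms the exact type I error is 11.7%, not the stated 9.7%. That is a separate matter; 11.7% is only the reference value here.
- Suppose 10%, 20% or 30% of true failures in each arm are rescued, exit before IMV and are scored successes. Recorded rates (active against SoC) become 82% v 55%, 84% v 60% and 86% v 65%. Power is 67.2%, 60.1% and 52.4%.
- If instead 5 or 10 percentage points of all patients are masked in each arm, power is 74.4% or 76.3%, so nothing is lost.
- If 5 points are masked in active and 10 in SoC, power is 62.8% and type I error 6.6%.

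**6. Why follow-up alone is not enough.** Suppose patients stay in the study but the scoring trigger is unchanged. Assume true success of 50% in both arms, 10% to 30% rescued before any IMV or ECMO, drug stopped in every rescued active patient, and half of the rescued alive on IMV or ECMO at Day 15. If active patients are scored at drug stop, recorded active success is 0.50 + 0.5r = 55% to 65%, against 50% for SoC. Masking of 5, 10 or 15 points moves type I error from 11.7% to 18.6%, 27.5% or 38.1%. This is an upper reading, because the rule does not clearly classify a patient who stops drug without IMV, stays in the study and is intubated by Day 15.

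**The case against.** The strongest reply is that part of the loss is already covered. The exit examination may record that day's status on the 7-point scale. SAEs are reportable to Week 10, including from other hospitals (5.5.4.3.4), and the Italian exemption letter covers fatal and life-threatening events in SoC. Worsening that prompts rescue will often itself be an SAE. In the illustration with such follow-up, the survival error is under one point (28.7% against 27.8%). This stands in part, so a reader should not infer that all deaths after rescue are lost. But no text says SAE collection continues after study withdrawal, and these routes give no discharge dates or routine last-alive dates. Catching deaths without survivors' dates turns the error upward.

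Two further replies stand. Every size above rests on assumed rescue and outcome rates. Survival and discharge are descriptive (7.3.1) and drive no decision rule.

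A reader might infer that primary scoring already favours the active arms. The documents do not support that: today rescue ends the study in every arm, so the two triggers coincide and scoring is roughly symmetric. The asymmetry would appear only if follow-up were kept and scoring left alone. Nor would that rescore every rescued SoC patient; it affects only those rescued before Day 15 whose status changes between exit and Day 15.

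**Conclusion.** The point holds. Rescue with one of these drugs removes patients from scheduled survival and discharge follow-up for a reason tied to prognosis, and lets a patient who exits before Day 15 without IMV or ECMO count as a primary success.

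The number of contacts lost (one to three) follows from the documents. The size of the bias does not. Under the stated assumptions the survival error runs from -9.0 to +5.1 points at 30% rescued, within sampling noise for 18 patients but systematic. Its direction is unknown: mortality is understated if nothing is learned after exit and overstated if only deaths are. The between-arm effect depends on which arm is rescued more. The primary-endpoint effect ranges from none to a fall in power to 52.4%, depending on how masking is spread.

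This merits correction mainly because the loss is avoidable at little cost. It does not show that the trial's decision rules are biased toward either drug.

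**What to change.** 1. In Protocol 5.4.7.2 and the synopsis, replace study withdrawal with mandatory withdrawal from study treatment under 5.3.3.1 and continued participation. The drugs stay prohibited alongside study drug. Unless consent is withdrawn, collect IMV/ECMO status to Day 15, and SAEs, special-interest events, vital status and discharge to Week 10, by telephone at Weeks 6 and 10 if needed.
2. In Protocol 7.3.8 and SAP 8.2.1 and 8.5.1, score patients in all three arms who start one of these drugs before Day 15 on their observed Day 15 IMV/ECMO and death status.

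Make both edits together, before the SAP is locked for the Stage 1 interim (SAP 5.2).

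Cost: one sentence in 5.4.7.2 and in the synopsis, a short edit to the scoring rule, no change in sample size, and a few more contacts of a kind already planned. Post-rescue outcomes, including Day 15 status, will partly reflect the rescue drug.

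The fix does not fully repair time to discharge, because SAP 8.5.2 also censors it at death. With 11 of 18 discharged and 4 dead by Day 28 (assumed), the Kaplan-Meier estimate under full follow-up could lie anywhere from 11/18 = 61.1% (deaths after the discharges) to 11/14 = 78.6% (deaths before them). That needs its own correction.

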5.4.8 Treatment compliance

The IMP administrations will be recorded in the CRF as described in Section 5.4.5.

Product accountability records will be kept. The pharmacy and Investigator must maintain accurate records demonstrating date and amount of study drug(s) received, to whom and by whom administered or dispensed (patient-by-patient accounting), and accounts of returned study drug (s) and any study drug accidentally or deliberately destroyed. All unused study drug will be counted.

At the end of the study, any remaining study drug (s) will be destroyed locally or returned to the depot for destruction. In either case, a certificate of destruction must be issued.

5.5 Efficacy and safety assessments

5.5.1 Study schedule

5.5.1.1 Schedule of events

Version 7.0 Final Protocol, Date 24 Jun 2020

Table 2 Schedule of Events

Emapalumab/Anakinra

	SCREENING	TREATMEN	T PERIOD		Early FU	FOLLOW-UP PERIOD				
ASSESSMENT	Up to 72h	Visit 1	Visit 2	Visit 3	Visit 4	Visit 5	Visit 6	Visit 7	Visit 8/TC	Visit 9/TC
	prior to Visit 1	Day 1 (Baseline)	Day 4	Day 7	Day 10	Day 13	Day 15 (± 1 day)	Day 28 (± 3 days)	Week 6 (± 5 days)	Week 10 (± 5 days)
Informed consent	х									
Eligibility criteria	Х	X1								
TB screening ¹³	х									
PCR SARS-CoV-2 ¹⁴	Х									
Patient information ²	х									
Symptom onset information	Х									
Physical examination ³	х									
Vital signs assessment ⁴	Х	Х	Х	Х	Х	Х	Х	Х		
ECG assessment	Х						Х	Х		
HRCT scan or X-ray of chest	X ⁵						Х	Х		
Laboratory assessments (local) ⁶	X ⁵	х	Х	Х	Х	Х	х	Х		
Urine pregnancy test ⁷	х						Х			
Randomization		х								
IMP administration ⁸		X					X			
Concomitant medication incl background therapy ⁹		x	х	х	х	х	х	x		
Pulmonary function ¹⁰		х	Х	Х	Х	Х	х	Х		
PaO ₂ /FiO ₂	Х						Х	Х		
Resting SpO ₂ (3 times per day)		Х	Х	Х	Х	Х	Х	X ¹⁸		
Hemogasanalysis		Х	Х	Х	Х	Х	Х	Х		
Oxygen supplementation		х	Х	Х	Х	Х	Х	Х		
MEWS score		х					Х	Х		
Clinical status 7 point ordinal scale		х	х	х	х	х	х	Х	х	Х

Confidential

Page 33 of 62

Clinical Study	No:	Sobi.IMMUNO-101
----------------	-----	-----------------

	SCREENING	TREATMEN	T PERIOD	Early FU	FOLLOW-UP PERIOD					
ASSESSMENT	Up to 72h prior to Visit 1	Visit 1	Visit 2	Visit 3	Visit 4	Visit 5	Visit 6	Visit 7	Visit 8/TC	Visit 9/TC
		Day 1 (Baseline)	Day 4	Day 7	Day 10	Day 13	Day 15 (± 1 day)	Day 28 (± 3 days)	Week 6 (± 5 days)	Week 10 (± 5 days)
Survival								х	Х	х
Time to hospital discharge								Х	Х	Х
Adverse events ¹¹		Х	Х	Х	Х	Х	Х	Х	Х	Х
Biomarkers ¹²		Х	Х	Х	Х	Х	Х	Х	Х	Х
PK: emapalumab/anakinra serum concentration ¹⁵		х	х	х	х	х	Х	х	х	х
Immunogenicity ¹⁶		х					Х	Х	Х	х
Viral shedding ¹⁷		х			Х		Х	Х	Х	Х

Abbreviations: CPAP, continuous positive airway pressure; ECMO, extracorporeal membrane oxygenation; FiO₂, fraction of inspired oxygen; HRCT, high resolution computed tomography; IMP, Investigational Medicinal Product; MEWS, modified early warning system; PaO₂, partial pressure of oxygen; SpO₂, peripheral capillary oxygen saturation During the treatment period (Days 1 to 15), clinical and laboratory assessments and procedures should preferably be performed before IMP administration. ¹Before study drug administration.

²Includes demographics, medical and surgical history and prior medication.

³Including recording of body weight and length.

⁴Body temperature, blood pressure, heart rate, respiratory rate and oxygen saturation.

⁵HRCT scan results and laboratory results already available in medical records at the time of informed consent can be used to confirm eligibility, if collected within 72 hours. ⁶Ferritin, LDH, D-dimers. WBC with differential counts, RBC, Hb, Platelet count, Fibrinogen, Complement C3/C4, Prothrombin Time, Cardiac troponin, AST, ALT, total bilirubin levels, CRP and Creatinine.

⁷Only applicable for females of childbearing potential.

⁸Emapalumab will be administered once daily Days 1, 4, 7, 10 and 13 (Section 5.4.5.1). Anakinra will be administered 4 times daily for 15 days i.e., Day 1 to 15 (Section 5.4.5.2). ⁹For details, see Section 5.4.7.

¹⁰Requirement for invasive mechanical ventilation or ECMO.

¹¹Incidence, severity, causality and outcomes of treatment-emergent serious AEs, adverse events leading to premature discontinuation of study treatment and adverse events of special interest.

¹² PD biomarkers: CXCL9, IFNy, IL-1, IL-6, sIL-2R. Samples to be collected Visit 1:pre-dose and thereafter at Visits 2, 3, 4, 5 and 6: end of infusion. (for anakinra treated patients; samples will only be collected in connection with the first infusion per day) In addition, at Visits 8 and 9, a PD biomarker sample will be collected in case the patient is coming to the clinic for these visits.

¹³Local TB testing to confirm patient status. Test result are accepted post randomization not to delay treatment.

Confidential

Page 34 of 62

Version 7.0 Final Protocol, Date 24 Jun 2020

Sobi

Emapalumab/Anakinra

Emapalumab/Anakinra

¹⁴Local PCR testing to confirm patient SARS-CoV-2 diagnosis. For sites where PCR is not part of hospital routine for confirming diagnosis/eligibility, test results are accepted post randomization not to delay treatment.

¹⁵ PK blood samples will be collected at Visit 1: pre-dose and at end-of infusion (for anakinra after the first infusion per day), and thereafter at Visits 2, 3, 4, 5 and 6: at end-of infusion (for anakinra treated patients; samples will only be collected in connection with the first infusion). In addition, for emapalumab treated patients at Visits 7. For Visit, 8 and Visit 9, a PK sample will be collected in case the patient is coming to the clinic for these visits.

¹⁶ Immunogenicity samples will be collected at Visit 1: Pre-dose and at Visit 6 at end-of infusion (for anakinra after the first infusion per day), and at Visit 7. For Visit 8 and Visit 9 immunogenicity samples will be collected in case the patient is coming to the clinic for these visits.

¹⁷ Viral shedding samples will be collected and stored for subsequent analysis.

 $^{18}\,$ If the patient is discharged before Visit 7, the resting SpO_2 is only required 1 time per day.

Page 35 of 62

5.5.1.2 Screening

Screening will occur up to 72 hours prior to Visit 1 (Baseline). The aim of the screening is to collect necessary data to confirm the patient's eligibility and can be ongoing up the randomization of the patient at Visit 1. A signed informed consent form must be obtained from the patient prior to any study-related activities. However, HRCT scan results and laboratory results already available in medical records at the time of informed consent can be used to confirm eligibility, if collected within 72 hours. Please refer to Table 3 for the clinical and laboratory parameters to be collected during screening.

Patients who do not meet the criteria for participation in this study (screening failure) may not be rescreened.

5.5.1.3 Visit 1, Baseline (Day 1)

Once all inclusion and exclusion criteria have been reviewed and recorded, and the patient has been found eligible, the patient will be randomized into one of the treatment groups and the first dose of study drug will be administered accordingly (see Section 5.4.5). Please refer to Table 2 for other clinical and laboratory parameters to be collected during the visit.

During the treatment period (Days 1 to 15), clinical and laboratory assessments and procedures should preferably be performed before IMP administration.

5.5.1.4 Visits 2 to 5 (Days 4, 7, 10 and 13)

Please refer to Table 2 for the clinical and laboratory parameters to be collected during these visits. For study drug administration schedule, see Section 5.4.5.

Effort should be made to adhere to the schedule of assessment. However, a window of ± 1 day will be allowed for all assessments scheduled for Visits 2 to 5. This does not include IMP administration.

During the treatment period (Days 1 to 15), clinical and laboratory assessments and procedures should preferably be performed before IMP administration.

